4.2. Primary Endpoint(s) Analyses

4.2.1. Definition of endpoint

Profile of patient-specific selection biomarkers that are targeted by therapeutics within the GSK oncology pipeline, as well as other study reference manual (SRM).

4.2.2. Main analytical approach

"Enrolled" analysis set will be used to perform primary endpoint analysis.

A summary table containing biomarker status of participants will be provided. Biomarker status includes Inducible T-cell Co-Stimulator (ICOS) status, New York esophageal squamous cell carcinoma 1 (NY-ESO-1)/Cancer testis antigen 2 (LAGE-1a) status and Programmed death protein 1 Ligand (PD-L1) status.

This summary table contains number and percentage of participants with positive/negative status by biomarker (ICOS, NY-ESO-1/LAGE-1a and PD-L1).

A subject level listing containing biomarker status of participants will also be provided.

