8.4.2. Other Analyse(s)

Demographic and baseline characteristics will be summarized by tumor type (i.e. NSCLC, HNSCC, breast, ovarian, CRC); and by clinical characteristics of interest to be described in a subsequent analysis plan. Medical history; history of cancer diagnosis and treatment; past and current medical conditions will be listed.

Percentage of participants and investigators utilizing the portal systems.

Results from single and multi-marker *in vitro* diagnostic assays will be summarized by tissue (i.e., tumor, blood) and tumor type.

HLA-subtypes for HLA-A locus will be listed and summarized by tumor type. Separate summaries of HLA-A may be given by ethnicity.

Number of participants who successfully provided a tumor sample will be summarized by tumor type. Separate summaries may be given by baseline demographics such as age and ethnicity.

Number of participants who have been referred into a treatment trial will be summarized by tumor type and treatment trial. Separate summaries may be given by baseline demographics such as age and ethnicity.

Treatment Patterns: Anti-cancer treatments received will be summarized for all participants stratified by tumor type and by line of therapy.

Time to Next Treatment (TTNT): The length of time from the initiation of an anticancer therapy to the date that the next systemic anticancer therapy is initiated. When subsequent treatment is not received, patients should be censored at last known activity (e.g. last physician visit).

Time to Progression (TTP): The length of time from the date the patient initiates an anticancer therapy to the date that a progression event or death due to progression is reported by the physician in the patient chart.

Overall Survival (OS): This is defined as the interval of time between the date of treatment initiation and the date of death due to any cause. For participants who do not

die, time of death will be censored at the date of last contact. Death due to any cause will be included.

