1.1.1. Objectives and Endpoints

[figure not shown]
Objectives	Endpoints	
Primary		
To evaluate molecular and immunological profile of tumor and peripheral blood of all enrolled participants, across indications and within tumor subsets (Building a GSK Clinical Science Database for tumor profiling and correlative studies).	Profile of patient specific selection biomarkers targeted by therapeutics with the GSK oncology pipeline, as well as other as detailed in the study reference manual (SRM).	
CCI		

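### The SAP's primary biomarker table and baseline summary have no tumor-type breakdown, although the primary objective and Protocol 8.4.2 call for one and SAP 4.7 declares no change

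*SAP*

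**What the plan says.** The primary objective, worded alike in Protocol 3 and SAP 1.1.1, is "To evaluate molecular and immunological profile of tumor and peripheral blood of all enrolled participants, across indications and within tumor subsets".

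Protocol 8.4.2 turns this into specific displays. On baseline data: "Demographic and baseline characteristics will be summarized by tumor type". It names the types as NSCLC, HNSCC, breast, ovarian and CRC. On in vitro assay results: "diagnostic assays will be summarized by tissue (i.e., tumor, blood) and tumor type". Four further by-tumor-type summaries follow in the same section.

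SAP 4.2.2 defines the primary analysis on the Enrolled set: "This summary table contains number and percentage of participants with positive/negative status by biomarker (ICOS, NY-ESO-1/LAGE-1a and PD-L1). A subject-level listing of biomarker status accompanies the table, with no mention of tumor type. SAP 6.1.2 summarizes age, gender, ethnicity, weight and race, with three age bands. SAP 4.1 limits summary tables to one study column unless stated otherwise. SAP 4.7 says the analysis planned in protocol amendment 3 is unchanged.

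**The concern.** As SAP 4.2.2 and 6.1.2 read, a programmer would produce one pooled column for each. That covers the all-enrolled part of the primary objective and leaves the tumor-subset part without a planned summary.

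The subset part matters for this study. Protocol 2.2.2.2 says NY-ESO-1 and LAGE-1a are expressed at different frequencies in different tumors, and gives analysis across tumor types as a way to improve trial design. A pooled positivity rate mixes those frequencies in proportions set by who happened to enroll. Without tumor-type counts in the baseline table, a reader of the report cannot see the mix or judge what the pooled rate represents.

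The statement in SAP 4.7 makes this more than a matter of brevity, because it tells the reader that nothing in the protocol's planned analysis was dropped.

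**Working it through.** **Step 1. Compare the documents.** There is no power or sample-size figure to reproduce: the 400 participants in Protocol 8.2 are an expectation with no statistical requirement behind it. The check is a comparison of Protocol 8.4.2 with the SAP.

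| Protocol 8.4.2 | SAP text available | Can it be judged? |
|---|---|---|
| Baseline characteristics by tumor type | 6.1.2: no tumor type | Yes, absent |
| Assay results by tissue and tumor type | 4.2.2: neither split | Yes, absent |
| "HLA-subtypes for HLA-A locus will be listed and summarized by tumor type" | No display seen | No, 4.4 not visible |
| "Number of participants who successfully provided a tumor sample will be summarized by tumor type" | No display seen | No, 4.4 not visible |
| "Number of participants who have been referred into a treatment trial will be summarized by tumor type and treatment trial" | No display seen | No, 4.4 not visible |
| "Anti-cancer treatments received will be summarized for all participants stratified by tumor type and by line of therapy" | No display seen | No, 4.4 not visible |

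Count: six in the protocol, none by tumor type in the public SAP, two of the six testable against a readable section.

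**Step 2. Is the omission declared?** SAP 4.1.1 drops by-centre summaries and gives thin accrual as the reason. No comparable statement covers tumor type. The single-column default in SAP 4.1 sets a layout, but it gives no reason and does not mention tumor type. SAP 4.7 declares no change.

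**Step 3. What a pooled percentage can hide.** The documents give no tumor-type shares, so both examples rest on assumed mixes. Neither is a forecast for this trial.

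- *Even split (assumption).* 400 participants over the five named areas gives 80 each.
  - Scenario A: 8/80 (10%) in every type, total 5 × 8 = 40.
  - Scenario B: 24/80 (30%) in one type and 4/80 (5%) in each of the other four, total 24 + 4 × 4 = 40, with 16/320 = 5% outside the first type.
  - Both give 40/400 = 10%, and the planned table cannot tell them apart.
- *Rates from Protocol 2.2.2.2.* About 76% positive in synovial sarcoma (NY-ESO-1) and roughly 10% in NSCLC (NY-ESO-1 and/or LAGE-1a). With an assumed sarcoma share s and the remainder NSCLC, pooled rate = 0.76 s + 0.10 (1 − s):

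| s | Calculation | Pooled |
|---|---|---|
| 0% | 0 + 0.100 | 10.0% |
| 5% | 0.038 + 0.095 | 13.3% |
| 10% | 0.076 + 0.090 | 16.6% |
| 20% | 0.152 + 0.080 | 23.2% |

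The pooled rate moves 6.6 points for each 10 points of case mix, with no change in either tumor's own rate. The two source rates use different marker definitions, and sarcoma is not one of the disease areas named in Protocol 5.1, so this shows only the mechanism.

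**Step 4. Are by-type figures usable?** Exact (Clopper-Pearson) 95% intervals at an observed 10%:

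| Count | 95% interval |
|---|---|
| 40/400 | 7.2–13.4% |
| 8/80 | 4.4–18.8% |
| 4/40 | 2.8–23.7% |
| 2/20 | 1.2–31.7% |

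They are usable as description and imprecise where a type is small.

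**The case against.** The strongest objection is that part of the SAP cannot be seen. Its numbering passes from 4.3 to 4.5, and a section between the secondary and safety analyses is a natural home for the protocol's other analyses. Text missing from the public version is not missing from the plan. This stands for the HLA, sample, referral and treatment summaries, so no omission is asserted for those four. It carries less weight for the primary display and the baseline summary, whose own sections are readable and do not point elsewhere.

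Second, SAP 1 confines the document to a synoptic report and disclosure, and the protocol foresees database work outside it. An analysis left out of a synoptic report need not have been withdrawn. That may well explain a shorter set of tables, but SAP 4.7 does not say so.

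Third, Protocol 8.4 stratifies key markers only where relevant, and the unconditional assay statement sits under other analyses rather than a primary analysis. That is a fair description of the structure. The qualifier is not attached to the statements in 8.4.2, however, and the objective itself names tumor subsets.

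Fourth, nothing is tested, no decision rule depends on the table, and a subject-level listing is planned. This limits the consequence. A listing that does not mention tumor type still does not replace a summary by tumor type.

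**Conclusion.** The concern holds for the two displays that can be checked. SAP 4.2.2 and 6.1.2 omit a breakdown that Protocol 8.4.2 states without condition and that the primary objective needs, and SAP 4.7 as worded does not match them.

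This should be fixed, but it is a reporting problem. Part of the primary objective would go unreported, and the pooled percentages could not be interpreted against the enrolled mix. It creates no false-positive risk. The numerical size for this trial is unknown because no tumor-type shares are given.

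Confidence is medium, because a by-type display could exist in SAP 4.4. In that case the remaining defect would be a missing cross-reference.

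**What to change.** - In SAP 4.2.2, report each biomarker's n/N and percentage by tumor type (NSCLC, HNSCC, breast, ovarian, CRC, other) beside the overall column, with N the number tested. Add tumor type to the biomarker listing.
- In SAP 6.1.2, add tumor-type counts to the baseline table and present the baseline summary by type as Protocol 8.4.2 states.
- If a by-type display already exists in SAP 4.4, refer to it from 4.2.2.
- If the synoptic report is meant to omit any Protocol 8.4.2 summary, including the split by tissue, state and justify that in SAP 4.7, as SAP 4.1.1 does for centres.

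The cost is SAP wording and a by-group run of tables already planned. No new data are needed: diagnosis is an entry requirement (Protocol 5.1, criterion 3), and disease history and characteristics are recorded at Visit 1 (Protocol 1.3). The drawback is small cells for some types, so the by-type figures should be labelled descriptive.

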4.3. Secondary Endpoint(s) Analyses

Not applicable, as there are no secondary endpoints defined under this protocol.

4.5. Safety Analyses

The safety analyses will be based on the Enrolled Analysis Set, unless otherwise specified.

Only the AEs/SAEs related to study procedures are collected in this study. If there are no AEs/SAEs in the database, a standard 'No data to report' display will be generated.

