Enrolled participants will be followed in two groups; (a) those enrolled onto a GSK clinical trial following Visit 3 and (b) those followed longitudinally, with disease reanalyzed at progression (Schedule of Activities Table 2). The total number of participants anticipated for this study is 400. Following consent, participants will have three initial study visits (further details on visits can be found in Schedule of Activities (SoA) and Section 4.1).

- **Visit 1:** Informed consent, review of medical history, targeted physical exam, information on Gather Share Know
- Visit 2: Biospecimen collection (e.g. tumor sample, blood), imaging
- **Visit 3:** Review results & trial matches with Physician, decide treatment options/treatment trial.

Note: Visit 1 and 2 may be combined, if appropriate, to reduce individual study visits. In the case that Visit 1 and 2 are combined, all corresponding samples must be collected per the SoA at this visit. In this scenario, following consent, all eligibility criteria should be confirmed prior to taking any Visit 2 assessments.

If a patient does not enroll onto a GSK study, or any other investigational study, the patient may remain under MDCI and be followed as per assessments on SoA Table 2.

Duration: It is expected that a majority of patients complete Visit 1 through Visit 3 in \leq 8 weeks; Participants who are followed longitudinally (SoA Table 2) may be followed for 2 years.

[figure not shown]
The study protocol will remain open until all designated GSK-sponsored impacted clinical trials (outlined in SRM) are closed to enrolment & all participants have completed this study or at the discretion of GSK.

Data Monitoring or Other Committee:

Study 213299 Translational Research Committee

This committee is composed of both internal and external disease-area experts. The objective of the Translational Research Committee for Study 213299 is to consult on trial design, development, and implementation of MDCI. Interim data will be reviewed to facilitate these efforts.

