5.3. Screen Failures

Screen failures are defined as participants who consent to participate in Study 213299 but are not subsequently entered in the study. A minimal set of screen failure information is required to ensure transparent reporting of screen failure participants to meet the Consolidated Standards of Reporting Trials (CONSORT) publishing requirements and to respond to queries from regulatory authorities. Minimal information includes demography, screen failure details, eligibility criteria, any protocol deviations and any serious adverse events (SAEs).

Individuals who do not meet the criteria for participation in this study (screen failure) may be rescreened.

All samples (tumor and blood) and radiographic imaging collected from screen failure participants may be used for further biomarker, companion diagnostic, disease characterization, and/or genetic research.

Consent to another intended treatment protocol and tumor reanalysis are allowed after discussion with Sponsor.

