7.5.1. Time Period and Frequency for Collecting AE and SAE Information

- All SAEs will be collected from at the time points specified in the SoA (Section 1.3). However, any SAEs assessed as related to study participation (e.g., protocol-mandated procedures, invasive tests, or change in existing therapy) or related to a GSK product will be recorded from the time a participant consents to participate in the study.
- All AEs will be collected at the time points specified in the SoA (Section 1.3).
- Medical occurrences that begin before the start of procedures but after obtaining informed consent will be recorded on the Medical History/Current Medical Conditions section of the case report form (CRF) not the AE section.
- All SAEs will be recorded and reported to the sponsor or designee immediately and under no circumstance should this exceed 24 hours, as indicated in Appendix 3.
- The investigator will submit any updated SAE data to the sponsor within 24 hours of it being available.
- Investigators are not obligated to actively seek AEs or SAEs after the conclusion of the study participation. However, if the investigator learns of any SAE, including a death, at any time after a participant has been discharged from the study, and he/she considers the event to be reasonably related to the study participation, the investigator must promptly notify the sponsor.

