3. ANALYSIS SETS

Analysis Set	Definition / Criteria	Analyses Evaluated	
Screened	All participants who sign the ICF	 Study population 	
Enrolled	All participants who sign the ICF and meet inclusion/exclusion criteria	Study Population Safety	

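### SAP safety tables use an eligibility-defined set, so SAEs collected from screen failures fall outside them, and the set for the AE listing is not stated

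*SAP*

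**What the plan says.** **Which set is used.** SAP Section 4.5: "The safety analyses will be based on the Enrolled Analysis Set, unless otherwise specified". SAP Section 3 defines Enrolled as "All participants who sign the ICF and meet inclusion/exclusion criteria" and Screened as "All participants who sign the ICF". Safety appears among the analyses for Enrolled only; Screened is assigned to study-population displays.

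**Which displays.** SAP Section 4.5.2 plans AE and SAE tables by SOC and PT, fatal and non-serious summaries, one listing of every AE collected with SAE flags, and separate listings of fatal and non-fatal SAEs. It names no analysis set for any of them.

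**What is collected.** For screen failures, protocol Section 5.3 says: "Minimal information includes demography, screen failure details, eligibility criteria, any protocol deviations and any serious adverse events (SAEs"). The same section foresees that material may already have been obtained from them: "All samples (tumor and blood) and radiographic imaging collected from screen failure participants may be used" for further research. Under protocol Section 7.5.1, SAEs assessed as related to study participation "will be recorded from the time a participant consents to participate in the study".

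**The concern.** No study drug is given. Protocol Section 2.3.1 names obtaining specimens as the main risk to patients. The people at risk are therefore those who underwent a procedure, whether or not they turned out to be eligible. A safety set defined by eligibility can exclude someone who was exposed and whose event is in the database.

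The SAP's displays feed the synoptic CSR and public disclosure (SAP Section 1). With few events expected, one omitted SAE could change what is reported. SAP Section 4.5 makes the effect visible: its empty-display rule is triggered when the database holds no AEs or SAEs. If the only SAE occurred in a screen failure, the database would not be empty, yet SAE tables restricted to Enrolled would show none.

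**Working it through.** The plan gives no figure to reproduce, so the check is mainly a comparison of definitions.

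**1. Screen failures.**
- Protocol Section 5.3 defines a screen failure as someone who consents but is not then entered. Such a person is in Screened and not in Enrolled.
- Their SAEs are required (protocol Section 5.3), and participation-related SAEs count from consent (protocol Section 7.5.1), before eligibility is settled.
- Every table in SAP Section 4.5.2 takes the Enrolled default, so these SAEs are in no table.
- The screen-failure displays in SAP Section 6.1.1 use the Screened set but cover status and reasons, not SAEs.

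**2. Sampled, later found ineligible.** Read literally, a person who breached a criterion does not satisfy "All participants who sign the ICF and meet inclusion/exclusion criteria" and drops out. If Enrolled means judged eligible at entry, the person stays in. The SAP does not say which applies.

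**3. Listings.** The general AE listing is described as covering everything collected, but no set is named. Where the SAP departs from Enrolled elsewhere (Section 6.1.1), it names the other set. The default therefore points to Enrolled, though the wording leaves room for the wider reading.

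**4. Does the protocol's own set close the gap?** No. The Safety population in protocol Section 8.3 requires enrolment and a tumor or blood sample, so it also excludes screen failures.

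**5. What can happen before eligibility is settled?**
- Visit 1 includes examination, vitals, ECG, and hematology, coagulation and infectious-disease bloods (protocol Section 1.3, Table 1).
- Biopsy, research bloods and tumor imaging belong to Visit 2. For combined visits the Synopsis says "following consent, all eligibility criteria should be confirmed prior to taking any Visit 2 assessments". Protocol Section 7 confirms eligibility from the Visit 1 evaluations.
- One criterion can fail later. Inclusion criterion 7 requires a negative pregnancy test within 24 hours before biopsy, while imaging may precede Visit 2 by up to 4 weeks (protocol Section 7.2.2).

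**6. Size, under assumptions.** The documents give no screen-failure rate *f*. With 400 enrolled (protocol Section 8.2), screened = 400/(1 − *f*).
- *f* = 5% (assumed): 400/0.95 ≈ 421, so about 21 failures.
- *f* = 20% (assumed): 400/0.80 = 500, so 100 failures.

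These are people, not SAEs. For scale, protocol Section 2.3.1 cites 26 grade 3 and 7 grade 4 biopsy events among 4,627 patients: 33/4,627 = 0.71%. As a rough stand-in for an SAE rate, and supposing every screen failure were biopsied:
- 21 × 0.0071 ≈ 0.15 events
- 100 × 0.0071 ≈ 0.7 events

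The schedule contradicts that supposition, so the realistic number of biopsy-related events in screen failures is lower still.

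**The case against.** **The listing may already cover these events.** A listing of every AE collected, with SAE flags, can be read as including screen failures. A reader might infer that such SAEs appear in no table or listing at all. The documents do not establish that: it is firm for the tables, and for the listings it rests on the Section 4.5 default. Nor do the events vanish, since they still go to the sponsor within 24 hours (protocol Section 7.5.1). The gap is in reported analysis.

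**Enrolled may simply mean entered.** SAP Section 6.2.1 anchors study day on an enrolment date, and Section 6.1.3 summarises important deviations. Both fit a reading in which later-found breaches are deviations and the person stays in the set. This stands as a plausible reading, which is why the second group is only conditionally affected. The screen-failure point does not depend on it.

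**Exposure before the eligibility check is light.** This largely stands. Performance status, ECG and history are Visit 1 items, and pregnancy is tested at study start and again before procedures. A reader might infer from the sentence on screen-failure samples that screen failures are biopsied. It only permits use of what was collected; archival tissue is the first-line specimen and involves no new procedure, and early imaging may be reused standard-of-care scans. But Visit 1 bloods are still protocol procedures, and the late pregnancy test leaves a route to failure after imaging.

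**The SAP did not create the gap.** Correct. Its Enrolled set is wider than the protocol's Safety population, because it drops the sample condition. That answers any charge that the SAP narrowed the protocol's set, but leaves the collected SAEs outside the tables.

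**Conclusion.** The point holds in limited form. As written, SAEs that the protocol collects from screen failures are excluded from every AE/SAE table. SAEs in participants sampled and later found ineligible are excluded too if the Enrolled definition is applied literally. Whether the AE listing includes either group is unstated, with the default pointing to Enrolled.

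The number of affected events is probably very small and cannot be derived from the documents. A reader might take the range of 21 to 100 people as a measure of lost safety information. It rests on an assumed failure rate and counts consented participants, most of whom would have no reportable event. The reason to act is that required data have no stated place in the report, and correcting this is cheap.

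**What to change.** In SAP Sections 3, 4.5 and 4.5.2:

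1. Keep the Enrolled set as denominator for the AE/SAE percentage tables.
2. State that anyone who was entered and underwent a protocol procedure stays in the safety set even if later found ineligible.
3. State that the AE/SAE listings cover all participants who signed the ICF (the Screened set), and amend the Screened row of Section 3 to show this use.
4. Flag SAEs in participants not in the Enrolled set, or give them a separate listing.

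This keeps one set for the percentages and one for the listings. The cost is SAP wording and one extra listing or flag, produced from data already collected.
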